### **6.3.8.2 Alkaline Phosphatase Activity**

Alkaline phosphatase activity will only be measured at baseline (pre-dose). Alkaline phosphatase activity results from blood samples taken during the first 14 days of the study are not to be reported to the study team members or to any other study staff member involved in the conduct of the study as it could lead to unblinding and to erroneous interpretation of liver function, as the recAP administered will increase the AP activity (see Section 5.6).

### **6.3.8.3 Pharmacokinetic Assessments**

Pharmacokinetic assessments will be performed during Part 1 only.

The following PK samples will be taken from Day 1 to Day 7 (inclusive) in the first 120 patients from Part 1 only and exact sampling clock times will be recorded:

- Day 1: One pre-dose sample and one post-dose sample near peak (approximately  $2.5 \pm 1.0$  hour after dosing).
- Day 2: One sample near trough ( $1.5 \pm 1$  hour before the second dose) and one sample near peak (approximately  $2.5 \pm 1.0$  hour after Day 2 dosing).\*
- Day 3: One sample near trough ( $1.5 \pm 1$  hour before the third dose) and one sample near peak (approximately  $2.5 \pm 1.0$  hour after Day 3 dosing).\*
- Day 4: One PK sample, random time.
- Day 5: One PK sample, random time.
- Day 6: One PK sample, random time.
- Day 7: One PK sample, random time.

#### **6.3.8.4 Immunogenicity Assessments**

The following immunogenicity assessments will be performed:

- IgG, IgE, and total immunoglobulin
- Anti-drug antibodies

Blood samples for IgG, IgE, and total immunoglobulin assessment will be taken at baseline and on Days 14 and 28 (see Section 13.1 [Table 13-1] and Section 13.2 [Figure 13-1]).

Blood samples for anti-drug antibodies assessment will be taken at baseline and on Days 14, 28, 60, and 90 (see Section 13.1 [Table 13-1] and Section 13.2 [Figure 13-1]). Samples taken on Days 60 and 90 will only be analyzed in case of a positive result on Day 28; however, as the results for Day 28 will not be available before Day 60, blood samples for anti-drug antibodies will be taken from all patients on Days 60 and 90. In case the results are negative on Day 14 and Day 28, samples taken on Days 60 and 90 will not be analyzed.

Assays for the determination of levels of circulating recAP (Section 6.3.8.3) and anti-drug antibodies were previously qualified in normal human serum samples according to validation procedures and acceptance of the Food and Drug Administration (FDA) Guidance for Industry, EMA guidelines and ICH guidelines for use in Phase 1 clinical trial (DHHS 2001, DeSilva et al 2003; EMA 2006; Neyer et al 2006; Shankar et al 2006; Viswanathan et al 2007; EMA 2007; EMA 2009; EMA 2011; ICH 2011). Additional qualification studies for both assays have been successfully completed in serum from sepsis patients under study plan AMF2013EL-14213-A for the determination of levels of circulating recAP and study plan AMF2013EL-14213-C for the determination of anti-drug antibodies, to support the use of the assays in the Phase 2 clinical study (AP-recAP-AKI-02-01).

#### **6.3.8.5 Biomarker Assessments**

Kidney function markers (e.g., urine and serum creatinine, BUN/urea clearance, sodium, proteinuria, fractional excretion of sodium and urea, and urine output), tubular injury biomarkers (e.g., KIM-1, IL-18, GST-alpha), and biomarkers for systemic inflammation (e.g., IL-6, CRP, LBP) will be measured during the duration of the study. Blood and urine samples will be collected at baseline, and at all visits from Day 1 to Day 28 (see Section 13.1 [Table 13-1] and Section 13.2 [Figure 13-1]).

Blood samples will be collected for the systemic inflammatory biomarkers: e.g., IL-6, CRP, and LBP.

Urine samples will be collected for the renal damage biomarkers: KIM-1, IL-18 and GST-alpha.

Any blood and urine samples not used for the biomarker assessments described will be stored by the central laboratory for a maximum of 1 year after the finalization of the study report to be possibly analyzed in an exploratory manner, in case new biomarkers are developed during the conduct of the study.

### **6.3.8.6 Pharmacodynamic Assessments**

For a limited number of sites only, a urine sample for PD assessment will be taken from the  $6 \pm 1$  hour urine collection see Section 13.5 (Appendix 5).

### **6.3.8.7 Glomerular Filtration Rate**

A limited number of sites only will simultaneously determine GFR with iohexol administration and blood sampling (considered the golden standard) to globally compare and assess correlation of GFR and calculated endogenous creatinine clearance. In addition, at these sites samples from the effluent from patients on RRT will be taken to assess exogenous (machine) creatinine clearance. Detailed instructions to these sites for iohexol and exogenous creatinine clearance are provided in Section 13.5.

## **6.3.9 Renal Replacement Therapy**

From Day 1 to Day 7 only continuous modalities of RRT are allowed. From Day 8 onward, intermittent/non-continuous modalities such as intermittent hemodialysis are allowed.

Initiation of RRT: Initiation of RRT should be based on the criteria described by Bellomo et al (2012).

Meeting at least one criterion of the below makes the patient eligible for initiation of RRT:

1. Anuria (negligible urine output for 6 hours)
2. Severe oliguria (urine output < 200 mL over 12 hours)
3. Hyperkalemia (potassium concentrations > 6.5 mmol/L)
4. Severe metabolic acidosis (pH < 7.2 despite normal or low partial pressure of carbon dioxide in arterial blood)

5. Volume overload (especially pulmonary edema unresponsive to diuretics)
6. Pronounced azotemia (urea concentrations > 30 mmol/L or creatinine concentrations > 300  $\mu$ mol/L)
7. Clinical complications of uremia (e.g., encephalopathy, pericarditis, neuropathy)

Timing of Stopping RRT: Termination of dialysis is based on criteria as used in the VA/NIH Acute Renal Failure Trial Network Study (VA/NIH Acute Renal Failure Trial Network, 2008). If (on continuous renal replacement therapy or between intermittent hemodialysis sessions) diuresis > 30 mL/hour and there are no other indications for RRT, then endogenous creatinine clearance should be calculated using a 6-hour urine collection period. If endogenous creatinine clearance  $\geq$  20 mL/min, RRT should be discontinued. If endogenous creatinine clearance  $\leq$  12 mL/min, RRT should be continued. If endogenous creatinine clearance > 12 mL/min and < 20 mL/min, continuation or termination will be the decision of the treating physician. Exact criterion or criteria, corresponding values (e.g., sodium, potassium, or pH) and deviations (e.g., RRT not started when indicated or RRT started when not indicated) need to be meticulously recorded in the eCRF.

However, although the criteria for starting and stopping mentioned above are strongly preferred within the protocol setting, based on clinical judgment investigators may deviate from these criteria. For example, several individual criteria might just not meet the required threshold, but together could provide a valid clinical reason to start RRT. It is also possible that an investigator decides not to initiate RRT based on clinical judgment, although starting criteria might be met. When RRT is initiated despite not meeting criteria, or when RRT is not initiated despite meeting criteria, this should be recorded and a reason for the clinical decision should be provided in the eCRF. Similarly, deviations from the protocol-defined stopping criteria, should be recorded in the CRF, together with the reason for the deviation. A worksheet will be provided as source to record decisions on initiation and termination RRT and deviations.

The following data will be collected in the eCRF:

- Requirement for RRT (over study period): RRT initiated (yes or no)
- Duration of RRT: Exact initiation and termination dates, times of dialysis, and reasons to initiate and terminate RRT. Temporary stopping of RRT need not be recorded (e.g., for filter failures or procedures requiring transportation such as computed tomography scan or others)
- Incidence of dialysis dependency at Day 60 and Day 90.

### **6.3.10 Lung Function Assessments**

Method of ventilation, e.g., non-rebreathing mask, non-invasive mechanical ventilation, invasive mechanical ventilation, will be recorded in the eCRF.

Details on mechanical ventilation will be measured to assess the patient's dependency on mechanical ventilation.

If the patient requires mechanical ventilation (invasive or non-invasive), the start and stop day and time will be recorded in the eCRF in order to calculate the number of days in which mechanical ventilation is needed. If modes of mechanical ventilation are changed (e.g. invasive mechanical ventilation is replaced with non-invasive continuous positive airway pressure (CPAP), a new eCRF page needs to be completed for new mode of mechanical ventilation.

During mechanical ventilation, arterial PaO2, FiO2, and PEEP, and during invasive mechanical ventilation only tidal volume will be captured as estimated daily averages at baseline and at all visits from Day 1 to Day 28 (see Section 13.1 [Table 13-1] and Section 13.2 [Figure 13-1]).

The fraction PaO2 /FiO2 will be measured to assess the degree of severity of lung function damage. Fraction PaO2/FiO2 will be calculated based on values which must be captured at the same time point. Only one simultaneous measurement will be used (i.e., do not use daily average). In case of multiple measurements of this fraction the worst value must be used.

### **6.3.11 Scoring Systems**

#### **6.3.11.1 Acute Physiology and Chronic Health Evaluation Score**

The APACHE II score is a severity-of-disease classification system, used in ICU or intermediate care unit settings. The score from 0 to 71 is computed on 12 physiological measurements. The higher the score the more severe the disease and higher the risk of death.

The APACHE II score will be assessed at baseline (i.e., not necessarily at ICU or intermediate care unit admission) and recorded in the eCRF.

### **6.3.11.2 Simplified Acute Physiology Score 2**

The SAPS-2 score is another severity-to-disease classification system, based upon 17 variables, including 12 physiological parameters.

The SAPS-2 score will be assessed at baseline and recorded in the eCRF.

### **6.3.11.3 Sequential Organ Failure Assessment Score**

The SOFA score provides a tool to quantify the severity of the patient's illness, based on the degree of organ dysfunction. The SOFA score is used to follow the condition of the patients in terms of organ failure over time.

The SOFA score will be assessed at baseline, and at all planned visits from Day 1 to Day 28 (as long as the patient is in the ICU or intermediate care unit ) and at discharge from ICU or intermediate care unit (see Section 13.1 [Table 13-1] and Section 13.2 [Figure 13-1]). Results will be recorded in the eCRF. Note that platelets, bilirubin, creatinine, and urine output are required to obtain a SOFA score.

### **6.3.11.4 Quality of Life**

The EQ-5D questionnaires will be performed at baseline, at discharge from ICU or intermediate care unit, and at Day 90 (see Section 13.1 [Table 13-1] and Section 13.2 [Figure 13-1]).

The EQ-5D covers 5 dimensions of general well-being. The questionnaire consists of 1 page with 5 questions and 1 page with an analog scale. The questionnaire should be completed by the patient. If the patient is not able to complete the questionnaire himself or herself (e.g., at baseline), it can be completed by a relative.

### **6.3.12 Concomitant Medication**

Concomitant medication will be checked at each visit and recorded in the eCRF.

Concomitant medication will be recorded at screening (verification that no concomitant medications that should be avoided are taken), and from baseline up to Day 28, inclusive (see Section 13.1 [Table 13-1] and Section 13.2 [Figure 13-1]).

For continuously intravenously administered medication (e.g., insulin, vasopressors, inotropics, diuretics, sedatives, metoprolol, and potassium), only the name, estimated mean daily dose or mean daily dose as calculated by the system will be recorded, and stop and start dates should be recorded in the eCRF for those patients who are in the ICU or intermediate care unit (see Section 5.7).

### **6.3.13 Other Collected Data**

The following data will also be collected during the study:

**Number of shock-free days:** measured with dates and times of treatment with inotropic agents or vasopressors – day and hour

**Length of ICU or intermediate care unit stay:** the admission date and planned and actual discharge date of the patient will be recorded.

**Length of hospital stay:** the admission date and planned and actual discharge date of the patient will be recorded. Reason for hospitalization will also be recorded.

### **6.3.14 Adverse Events**

The investigator is responsible for reporting all treatment-emergent AEs (TEAEs) that are observed or reported during the study, regardless of their relationship to study drug or their clinical significance.

#### **6.3.14.1 Definitions of Adverse Events**

An AE is defined as any untoward medical occurrence (e.g., symptom, sign, diagnosis or diagnostic test finding) in a patient enrolled into a clinical study regardless of its causal relationship to study drug.

A TEAE is defined as any event not present before exposure to study drug or any event already present that worsens in either intensity or frequency after exposure to study drug.

An SAE is defined as any event that results in death, is immediately life threatening, requires inpatient hospitalization or prolongation of existing hospitalization, results in persistent or significant disability/incapacity, or is a congenital anomaly/birth defect. Important medical events that may not result in death, be life threatening, or require hospitalization may be

considered SAEs when, based upon appropriate medical judgment, they may jeopardize the patient or may require medical or surgical intervention to prevent one of the outcomes listed in this definition. Medical and scientific judgment should be exercised in deciding whether expedited reporting is appropriate in other situations, such as important medical events that may not be immediately life threatening or result in death or hospitalization but may jeopardize the patient or may require intervention to prevent one of the other outcomes listed in the aforementioned definition. These should also be considered serious. A death occurring during the study or which comes to the attention of the investigator until Day 28 visit, whether considered treatment related or not, must be reported as an SAE. In the event of an SAE the investigator may immediately stop treatment (during the treatment phase, i.e., the first 3 days of the study) if it is considered in the best interest of the patient. In case study drug is discontinued early, the patient will continue follow-up in the study as per protocol. If interrupted for any reason, re-starting of study drug should be discussed with the Medical Monitor (see Section 4.2.1).

Any medical condition that is present at the time that the patient is screened but does not deteriorate should not be reported as an AE. However, if the medical condition deteriorates at any time during the study, it should be recorded as an AE.

#### **6.3.14.2 Eliciting and Documenting Adverse Events**

Adverse events will be collected and assessed from the time the patient signs the ICF until Day 28 visit for all AEs (including SAEs) regardless of its relationship to study drug. Any AE that occurs during or after the first dose of study drug is considered treatment emergent.

At every study visit, patients will be asked a standard non-leading question to elicit any medically related changes in their well-being. At follow-up visits, they will also be asked if they have been admitted to the hospital, had any accidents, used any new medications, or changed concomitant medication regimens.

When patients have left the hospital they will be instructed to contact the investigator at any time if any symptoms develop.

Adverse events and SAEs that occur after Day 28 visit, will be reported to PPD or sponsor, only if the investigator considers them possibly, probably, or definitely related to study drug.

In addition to patient accounts, AEs will be identified through physical examination, review of laboratory values, diagnostic test findings (Section 6.5) and monitoring in the ICU/healthcare facility and (if relevant) report from carers..

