### 7.3.2 Other Organs

Endpoints for organs other than renal function include the following:

- Liver enzymes (AST, ALT, GGT, LDH, bilirubin but excluding AP).
- Lung function as assessed by arterial PaO2, FiO2, P/F ratio, PEEP, and tidal volume in mechanically ventilated patients.
- Ventilator-free days (from Day 1 to Day 28, inclusive), i.e., 28 days minus the number of days a patient is on ventilator during this period. Should a patient die or withdraw prior to Day 28, the days remaining in this period will be counted as per the status of the patient at time of death or withdrawal.
- Time from start of first administration of study drug to being off-ventilator (from Day 1 to Day 28, inclusive) for those patients who are on ventilator at the start of this period. Patients who remain on ventilator will be censored at the earliest of Day 28 or withdrawal from the study for any reason.
- Shock-free days (during the period Day 1 to Day 28, inclusive), i.e., 28 days minus the number of days a patient is on inotropic or vasopressor therapy during this period. Should a patient die or withdraw prior to Day 28, the days remaining in this period will be counted as per the status of the patient at time of death or withdrawal. A patient is considered to be shock free if he or she is not on vasopressors or inotropic agents (including but not limited to noradrenaline, adrenaline, dobutamine, dopamine, vasopressin, and enoximone).
- Time from start of first administration of treatment to being shock free (from Day 1 to Day 28, inclusive) for those patients who are not shock free at the start of this period. Patients who do not become shock free will be censored at the earliest of Day 28 or withdrawal from the study for any reason.
- SOFA scores during ICU or intermediate care unit stay.
- Number of dysfunctional organs as assessed by SOFA scores.
- Deaths during the 90-day study period (by recording date).

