**14.1.3 Change Number 3**

Safety reporting requirements in Section 6.3 and Sections 6.3.14 to 6.5 (inclusive) have been amended in the study protocol and all exemptions to AE or SAE reporting have been removed. Consequently, investigators will be required to report all AEs, regardless of causality, occurring since the informed consent form has been signed until Day 30 after last dose of study drug or later for events possibly, probably, or definitely related to study drug.

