6.4. Inclusion and Exclusion Criteria

A listing, based on the all Enrolled Set, will be included displaying which protocol version/amendment each patient was recruited under, and whether the patient met and/or did not meet the inclusion and exclusion criteria.

7. Treatments and Medications

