9.1.6. Death

For patients who died any time during the study or during follow-up, their cause of death will be categorized and presented by SOC, PT. A listing of all deaths and associated cause of death will be provided as well. All death will be coded using MedDRA Version 16.1 or later.

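### Adverse event tables and the cause-of-death table have no cut-off at the Day 28 visit, where the protocol's reporting rule changes

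*Protocol*

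**What the plan says.** Protocol 6.3.14.2 collects events from consent "until Day 28 visit for all AEs (including SAEs) regardless of its relationship to study drug". For the time after that visit it says: "Adverse events and SAEs that occur after Day 28 visit, will be reported to PPD or sponsor, only if the investigator considers them" to have at least a possible link with the drug. The same section treats any event during or after the first dose as treatment emergent.

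The SAP defines a treatment-emergent event in 9.1 by its start relative to exposure and sets no end. The summaries in 9.1.1 (incidence), 9.1.2 (relationship), 9.1.3 (severity) and 9.1.4 (serious events) add no onset limit.

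On deaths, SAP 9.1.6 states: "For patients who died any time during the study or during follow-up, their cause of death will be categorized and presented by SOC, PT". The SAP change history shows that deaths during follow-up were added in version 3.0. Protocol 6.3.14.1 requires SAE reporting, related or not, for "A death occurring during the study or which comes to the attention of the investigator until Day 28 visit". Protocol 7.3.2 defines the 90-day death endpoint by date only.

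**The concern.** A table of event rates means something only if every row was collected under one rule. Here the rule changes at the Day 28 visit, but the tables do not. A related event on Day 45 satisfies the SAP definition and would be counted. An unrelated event of the same severity on the same day would not have been collected. The incidence and SAE percentages then have no clear observation period, and the relationship table includes a period in which only one answer can appear.

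The cause-of-death table has a related weakness. It extends through follow-up, but the protocol does not clearly secure the cause of an unrelated death after Day 28. Safety and tolerability are a secondary objective, and the protocol weighs safety in choosing the dose, so readers will rely on these tables.

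**Working it through.** The documents give no event rates, so the check is mainly a comparison of passages, with two small calculations.

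1. Share of follow-up under the narrower rule. Inputs: Day 28 visit ± 3 days and Day 90 visit ± 10 days (protocol 3.1; SAP section 4).
   - Nominal: Days 29 to 90 are 90 − 28 = 62 days, and 62/90 = 69%. Complete collection covers 28/90 = 31%.
   - Smallest share: visit on Day 31, last visit on Day 80. 80 − 31 = 49 days, and 49/80 = 61%.
   - Largest share: visit on Day 25, last visit on Day 100. 100 − 25 = 75 days, and 75/100 = 75%.

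2. Direction of the effect on the relationship table. SAP 9.1.2 counts a patient once, at the most related event. Let n patients have an event by the Day 28 visit, r of them a related one. After the visit only related events can be added. Suppose they move a patients from unrelated to related, and bring in b patients who had no event before. The related share goes from r/n to (r + a + b)/(n + b). The difference is [n·a + b·(n − r)] / [n·(n + b)], which is never negative. So the split can move only towards related. The size depends on a and b, which the documents do not give.

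3. Whether late related events reach the tables.
   - Protocol 6.3.14.3 limits the AE page of the eCRF to events up to the Day 28 visit, and 6.3.14.2 speaks only of reporting later ones to the CRO or sponsor. This suggests that they stay out of the analysis data.
   - Protocol 6.3.14.6 wants all AEs on the eCRF with no time limit. Section 6.3.14 makes the investigator responsible for all treatment-emergent events "that are observed or reported during the study, regardless of their relationship to study drug or their clinical significance". This suggests that they come in.
   - The SAP does not settle the question.

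4. An unrelated death on, say, Day 50.
   - Fact and date: recorded. Protocol 6.2.4 monitors mortality throughout, and 7.3.2 covers 90 days.
   - SAE report under 6.3.14.1: required if the study runs to Day 90 (section 4.2), not required if it ends at Day 28 (section 6.1.3).
   - SAE report under 6.3.14.2: not required, because the event is unrelated and after the Day 28 visit.
   - Row in the SAP 9.1.6 table: required.

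   So the table calls for a cause that no reporting rule clearly obliges the site to supply.

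5. What is not touched. SAP 8.2.2.2 counts deaths at fixed days, 28 and 90, from the fact and date of death. The treatment-discontinuation table (SAP 9.1.5) also lacks a cut-off, but dosing covers only Days 1 to 3, so late events can hardly enter it.

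**The case against.** Full collection to a fixed visit followed by related-only reporting is a deliberate design choice, and the AE-page rule in 6.3.14.3 may already keep late events out of the tables. With dosing on three days, and AP activity expected back to normal after Day 14 (protocol 5.6), few events after Day 28 are likely to be judged related. On deaths, sections 4.2, 7.3.2 and 10.3 all take the study past Day 28. On that reading 6.3.14.1 already requires every death to Day 90 as an SAE, and SAP 9.1.6 plans a listing of all deaths with cause.

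Much of this stands. The mixing is conditional, and its size may be small. It does not remove the point: the SAP contains no rule that would exclude a late related event, and sections 6.1.3 and 6.3.14.2 conflict with the longer reading on deaths.

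A reader might infer more than the documents support:

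- That 69% measures the harm. It is a share of calendar days, not of events.
- That the arms are biased against each other. The related-only rule applies to every arm under blinding.
- That dropped-dose arms have higher rates by construction, because patients under Protocol Version 2.0 had a longer window ("until Day 30 after last dose of study drug or later" for related events). That wording is superseded. The documents do not say how many patients were followed under it, or whether they moved to the current rule. SAP 9.1.1 counts a patient once at each level, so extra days raise a percentage only for a patient whose first such event falls in them.
- That causes listed after Day 28 will be mainly drug-attributed. Under the Day 90 reading they would be complete.

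**Conclusion.** The point holds as a minor one. The SAP's treatment-emergent, SAE, severity and relationship tables have no onset cut-off, although the reporting rule changes at the Day 28 visit. If late related events enter the analysis database, those tables mix two kinds of reporting and the relationship split shifts towards related. That condition is open in the documents. The number of affected events cannot be computed from them and may be small, and no bias between arms is shown.

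The cause-of-death problem does not depend on that condition. The protocol is inconsistent on whether an unrelated death after Day 28 must be reported as an SAE with its cause, and the SAP tabulates that cause regardless. How many deaths this concerns is not given. Mortality counts at Day 28 and Day 90 are sound.

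**What to change.** In SAP 9.1, restrict the treatment-emergent, SAE, severity and relationship tables to onset up to each patient's Day 28 visit, or to Day 28 where there was no visit. The cut should follow the visit, because the visit is where collection changes and it can fall anywhere from Day 25 to Day 31. List later related events separately.

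In SAP 9.1.6, split the cause-of-death table into deaths up to Day 28 and deaths on Days 29 to 90.

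In the protocol, reconcile 6.3.14.1, 6.3.14.2, 4.2 and 6.1.3 so that every death to Day 90 is recorded with its cause regardless of relationship.

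The SAP part costs some wording, one onset-date filter and one extra listing. The protocol part is one clarifying sentence, plus a cause field for late deaths if the death page lacks one. As an amendment it would go through the approvals in protocol 10.2.1. If data collection is already complete, the SAP changes can be made alone, with missing causes shown as missing.
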